6.2.2 Antitumor Effect

6.2.2.1 Response Criteria

Response criteria will be those specified by Cheson, et al [19] as the Revised Response Criteria for Malignant Lymphoma. Please refer to Table 6 for a tabular summary of the below definitions.

6.2.2.1.3 Complete Remission (CR):

The designation of CR requires the following (Table 6):

1. Complete disappearance of all detectable clinical evidence of disease and disease-related symptoms, if present before therapy.

2a. A post-treatment residual mass of any size is permitted as long as it is PET negative.

2b. If a pretreatment PET scan was negative, all lymph nodes and nodal masses must have regressed on CT to normal size (≤ 1.5 cm in their greatest transverse diameter for nodes > 1.5 cm before therapy). Previously involved nodes that were 1.1 to 1.5 cm in their long axis and more than 1.0 cm in their short axis before treatment must have decreased to ≤ 1.0 cm in their short axis after treatment.

3. The spleen and/or liver, if considered enlarged before therapy on the basis of a physical examination or CT scan, should not be palpable on physical examination and should be considered normal size by imaging studies, and nodules related to lymphoma should disappear. However, determination of splenic involvement is not always reliable because a spleen considered normal in size may still contain lymphoma, whereas an enlarged spleen may reflect variations in anatomy, blood volume, the use of hematopoietic growth factors, or causes other than lymphoma.

6.2.2.1.4

Partial Response (PR):

The designation of PR requires all of the following:

1. At least a 50% decrease in sum of the product of the diameters (SPD) of up to six of the largest dominant nodes or nodal masses. These nodes or masses should be selected according to all of the following: they should be clearly measurable in at least 2 perpendicular dimensions; if possible they should be from disparate regions of the body; and they should include mediastinal and retroperitoneal areas of disease whenever these sites are involved.

2. No increase should be observed in the size of other nodes, liver, or spleen.

3. Splenic and hepatic nodules must regress by $\geq 50\%$ in their SPD or, for single nodules, in the greatest transverse diameter.

4. With the exception of splenic and hepatic nodules, involvement of other organs is usually assessable and no measurable disease should be present.

5. Bone marrow assessment is irrelevant for determination of a PR if the sample was positive before treatment. However, if positive, the cell type should be specified (eg, large-cell lymphoma or small neoplastic B cells). Patients who achieve a CR by the above criteria, but who have persistent morphologic bone marrow involvement, will be considered partial responders. When the bone marrow was involved before therapy and a clinical CR was achieved, but with no bone marrow assessment after treatment, patients should be considered partial responders.

6. No new sites of disease should be observed.
7. If the PET scan was positive before therapy, the post-treatment PET should be positive in at least one previously involved site.
8. If the pretreatment PET scan was negative, CT criteria should be used.

6.2.2.1.5 **Stable Disease (SD):**
Stable disease (SD) is defined as the following:

1. A patient is considered to have SD when he or she fails to attain the criteria needed for a CR or PR, but does not fulfill those for progressive disease (see “Relapsed Disease [after CR]/Progressive Disease [after PR, SD],” below).
2. The PET should be positive at prior sites of disease with no new areas of involvement on the post-treatment CT or PET.
3. If the pretreatment PET was negative, there must be no change in the size of the previous lesions on the post-treatment CT scan.

6.2.2.1.6 **Relapsed Disease (after CR)/Progressive Disease (after PR, SD)**
Lymph nodes should be considered abnormal if the long axis is more than 1.5 cm regardless of the short axis. If a lymph node has a long axis of 1.1 to 1.5 cm, it should only be considered abnormal if its short axis is more than 1.0. Lymph nodes $\leq 1.0 \times \leq 1.0$ cm will not be considered as abnormal for relapse or progressive disease.

1. Appearance of any new lesion more than 1.5 cm in any axis during or at the end of therapy, even if other lesions are decreasing in size. Increased FDG uptake in a previously unaffected site should only be considered relapsed or progressive disease after confirmation with other modalities. In patients with no prior history of pulmonary lymphoma, new lung nodules identified by CT are mostly benign. Thus, a therapeutic decision should not be made solely on the basis of the PET without histologic confirmation.
2. At least a 50% increase from nadir in the SPD of any previously involved nodes, or in a single involved node, or the size of other lesions (eg, splenic or hepatic nodules). To be considered progressive disease, a lymph node with a diameter of the short axis of less than 1.0 cm must increase by $\geq 50\%$ and to a size of 1.5×1.5 cm or more than 1.5 cm in the long axis.
3. At least a 50% increase in the longest diameter of any single previously identified node more than 1 cm in its short axis.

4. Lesions should be PET positive if disease lesions were PET positive before therapy, unless the lesion is too small to be detected with current PET systems (<1.5 cm in its long axis by CT). Measurable extranodal disease should be assessed in a manner similar to that for nodal disease. For these recommendations, the spleen is considered nodal disease. Disease that is only assessable (eg, pleural effusions, bone lesions) will be recorded as present or absent only, unless, while an abnormality is still noted by imaging studies or physical examination, it is found to be histologically negative.

Table 6

Response	Definition	Nodal Masses	Spleen, Liver	Bone Marrow
CR	Disappearance of all evidence of disease	(a) FDG-avid or PET positive prior to therapy; mass of any size permitted if PET negative (b) Variably FDG-avid or PET negative; regression to normal size on CT	Not palpable, nodules disappeared	Infiltrate cleared on repeat biopsy; if indeterminate by morphology, immunohistochemistry should be negative
PR	Regression of measurable disease and no new sites	≥ 50% decrease in SPD of up to 6 largest dominant masses; no increase in size of other nodes (a) FDG-avid or PET positive prior to therapy; one or more PET positive at previously involved site (b) Variably FDG-avid or PET negative; regression on CT	≥ 50% decrease in SPD of nodules (for single nodule in greatest transverse diameter); no increase in size of liver or spleen	Irrelevant if positive prior to therapy; cell type should be specified
SD	Failure to attain CR/PR or PD	(a) FDG-avid or PET positive prior to therapy; PET positive at prior sites of disease and no new sites on CT or PET (b) Variably FDG-avid or PET negative; no change in size of previous lesions on CT		
Relapsed disease or PD	Any new lesion or increase by ≥ 50% of previously involved sites from nadir	Appearance of a new lesion(s) > 1.5 cm in any axis, ≥ 50% increase in SPD of more than one node, or ≥ 50% increase in longest diameter of a previously identified node > 1 cm in short axis Lesions PET positive if FDG-avid lymphoma or PET positive prior to therapy	> 50% increase from nadir in the SPD of any previous lesions	New or recurrent involvement

Abbreviations: CR, complete remission; FDG, [¹⁸F]fluorodeoxyglucose; PET, positron emission tomography; CT, computed tomography; PR, partial remission; SPD, sum of the product of the diameters; SD, stable disease; PD, progressive disease.

6.2.2.2 Evaluation of Best Overall Response
 The best overall response is the best response recorded from the start of the treatment until disease progression/recurrence (taking as reference for progressive disease the smallest measurements recorded since the treatment started). The patient's best response assignment will depend on the achievement of both measurement and confirmation criteria.

Target Lesions	Non-Target Lesions	New Lesions	Overall Response	Best Response for this Category Also Requires:
CR	CR	No	CR	≥ 4 wks. confirmation
CR	Non-CR/Non-PD	No	PR	≥ 4 wks. confirmation
PR	Non-PD	No	PR	
SD	Non-PD	No	SD	documented at least once ≥ 4 wks. from baseline
PD	Any	Yes or No	PD	no prior SD, PR or CR
Any	PD*	Yes or No	PD	
Any	Any	Yes	PD	

* In exceptional circumstances, unequivocal progression in non-target lesions may be accepted as disease progression.

Note: Patients with a global deterioration of health status requiring discontinuation of treatment without objective evidence of disease progression at that time should be reported as "*symptomatic deterioration*". Every effort should be made to document the objective progression even after discontinuation of treatment.

Note: If subjects respond to treatment and are able to have their disease resected, the patient's response will be assessed prior to the surgery.

6.2.3 Duration of Response

6.2.3.1 Duration of overall response:

The duration of overall response is measured from the time measurement criteria are met for CR or PR (whichever is first recorded) until the first date that recurrent or progressive disease is objectively documented (taking as reference for progressive disease the smallest measurements recorded since the treatment started).

The duration of overall CR is measured from the time measurement criteria are first met for CR until the first date that recurrent disease is objectively documented.

6.2.3.2 Duration of stable disease:

Stable disease is measured from the start of the treatment until the criteria for progression are met, taking as reference the smallest

measurements recorded since the treatment started.

6.2.3 Progression-Free Survival

Progression-free survival (PFS) is defined as the duration of time from start of treatment to time of progression. PFS will be documented based on clinical follow-up. Results of imaging studies conducted for clinical purposes will be documented, but the nature (eg, PET vs. CT) and frequency is at the discretion of the treating physician (apart from PET/CT obtained after Induction and Consolidation phases, which are mandatory).

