NCI	National Cancer Institute
NHL	Non-Hodgkin Lymphoma
ORR	Overall Response Rate
OS	Overall Survival
PBMCs	Peripheral Blood Mononuclear Cells
PD	Progressive Disease
PFS	Progression Free Survival
p.o.	per os/by mouth/orally
PR	Partial Response
PRR	Partial Response Rate
RP2D	Recommended phase II dose
QOD	Every other day
SAE	Serious Adverse Event
SD	Stable Disease
SGOT	Serum Glutamic Oxaloacetic Transaminase
SPGT	Serum Glutamic Pyruvic Transaminase
WBC	White Blood Cells

STUDY SCHEMA

- DLT period (Phase I only): 21 days of induction
- Duration of treatment (Phase I and II): one year, or until POD (whichever occurs first)
- Primary objective assessment: toxicity after week 4 treatment (Phase I only); scans after induction treatment and/or after consolidation treatment (if applicable) (Phase II only)

*This may be repeated once at discretion of treating investigator; see Section 4.0 (TREATMENT PLAN) for details.

DOSING SCHEMA (in weeks, continued for one year total, or until POD)

STUDY SUMMARY

Title	A Phase I-II Trial of Brentuximab Vedotin Plus Rituximab as Frontline Therapy for Patients with Lymphomas of Immunosuppressed States
Version Date	June 14, 2017 (Amendment 8)
Protocol Number	NU 12H09
Phase	I/II
Methodology	Open-label, single-arm
Study Duration	Approximately 30 months
Study Center(s)	Northwestern University, University of Chicago
Objectives	
Primary objectives: Phase I: Evaluate the safety of brentuximab vedotin and rituximab in patients with immunosuppressed lymphoid malignancies and to determine the recommended phase II dose (RP2D) of the combination. Phase II: Evaluate the efficacy of brentuximab vedotin and rituximab in patients with immunosuppressed lymphoid malignancies.
 
Secondary objectives: Phase II:
 
 1. Further evaluate the frequency and severity of toxicity. 2. Further evaluate the efficacy as measured by one-year PFS and OS. 3. Determine the effects of the combination of brentuximab vedotin and rituximab on markers of EBV activation and proliferation. 4. Further evaluate efficacy as measured by time to initiation of cytotoxic chemotherapy. 5. Further evaluate efficacy as measured by observed rates of graft rejection. 
Exploratory objectives (Phase I and II): Correlate response and outcomes with CD30 expression and EBV markers and levels.

Number of Subjects	Phase I: 3-9 patients; Phase II: 24 patients

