As noted above, up-front use of aggressive cytotoxic chemotherapy has been plagued by early TRM and graft rejection, and further clinical experience has suggested that a delayed introduction of aggressive chemotherapy may significantly reduce risks of TRM. For instance, a European cooperative group experience demonstrated the apparent advantage of a rituximab-based risk-stratified sequential treatment (RSST) strategy for PTLD patients [1]. In this model, all patients with a new diagnosis of PTLD are treated with 4 doses of weekly rituximab, followed by re-staging. Those with a complete response (CR) then receive an additional four doses of weekly rituximab, followed by observation, while those with any other response receive four cycles of R-CHOP-21. Among the first 40 patients treated, there was a 93% ORR, with 32% of patients able to avoid cytotoxic chemotherapy, and perhaps most notably, with rates of TRM (1/40 patients) that compare very favorably to historical rates. The potential clinical advantages to limiting exposure to cytotoxic chemotherapy have also been recognized in pediatric PTLD [37]. Also as noted above, most cases of non-transplant autoimmune-related lymphoma are indolent histology [19]. There is little or no data to establish R-CHOP as frontline therapy for such patients, and anthracycline is potentially “over-treatment” for indolent lymphomas in non-immunocompromised hosts [38].

We therefore hypothesize that brentuximab vedotin and rituximab, used together for the upfront treatment of EBV-related lymphoid malignancies, would optimize efficacy as compared to historical controls by A) improving response rates as compared to single-agent rituximab; B) reducing exposure to cytotoxic therapy, and thereby reduce rates of TRM; and C) ultimately improving PFS and OS. We propose a RSST strategy, similar to that described above, such that those patients failing to achieve a PR or CR to combined brentuximab vedotin and Rituximab therapy can then be treated with cytotoxic chemotherapy, with or without additional mAb therapy. Whereas we predict that EBV positivity may predict for response to anti-CD30 therapy, and that targeting of CD20 will serve to effectively deplete the EBV reservoir, tumor samples need express neither in order to enroll.

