2.2 Secondary Objectives (Phase II only)

- 2.2.1 To further evaluate the frequency and severity of toxicity.
- 2.2.2 To further evaluate the clinical efficacy of the combination of brentuximab vedotin and rituximab, as measured by PFS and OS at one year after the end of treatment.
- 2.2.3 To evaluate the best response to therapy.
- 2.2.4 To determine the effects of the combination of brentuximab vedotin and rituximab on markers of EBV activation and proliferation.
- 2.2.4 Further evaluate efficacy as measured by time to cytotoxic chemotherapy.
- 2.2.5 Further evaluate efficacy as measured by observed rates of graft rejection.

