2.3 Primary Endpoints

- 2.3.1 The primary endpoint for phase I, dose-limiting toxicity (DLT) will be defined as the occurrence of toxicity as detailed in section 4.2 (using CTCAE v 4.03), experienced during the first 3 weeks of study treatment. The MTD, which constitutes the RP2D, will be defined as described in Section 11 (Study Design).
- 2.3.2 The primary endpoint for phase II, response after induction or induction/consolidation, will be defined as the detection of SD, PR, or CR by CT or PET/CT, and/or resolution of marrow-only involvement. CR and PR will each be assessed according to the Revised Response Criteria for Malignant Lymphoma. Assessments will be performed after induction and/or consolidation treatment (if applicable).

2.4 Secondary Endpoints:

- 2.4.1 Adverse events will be defined as those included in CTCAE v 4.03. The occurrence and severity of each will be recorded.
- 2.4.2 PFS will be defined as the time elapsed between treatment initiation and tumor progression or death from any cause (whichever occurs first), with censoring of patients who are lost to follow-up. OS will be defined as freedom from death by any cause.
- 2.4.3 Best response will be assessed by CT or PET/CT according to the Revised Response Criteria for Malignant Lymphoma after induction and/or consolidation (if applicable) and every 12 weeks during maintenance treatment.
- 2.4.4 EBV activation and proliferation will be measured by viral loads as measured at time of enrollment and monthly thereafter in all enrolled patients, until completion of study therapy.
- 2.4.5 Time to initiation of cytotoxic chemotherapy will be defined as the time elapsed between treatment initiation, and time of first non-targeted cytotoxic chemotherapy.
- 2.4.6 Graft rejection will be defined as any of the following: documentation of new or progressive rejection by tissue biopsy of the graft; re-transplantation due to graft rejection; clinical diagnosis of new or progressive graft rejection, since start of treatment on protocol, as given by the patient's transplant physician. Escalation of intensity of immunosuppression will not, by itself, be considered evidence of graft rejection. (Note: patients with clinically active graft rejection will not be excluded from trial enrollment, but will not be considered to have treatment-emergent graft rejection unless progression of rejection is documented.)

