2.6 Exploratory Endpoints

Levels of CD30 expression, EBV proliferation, and tumor proliferation (ie, Ki-67), all obtained from TMAs performed on pre-treatment tissue samples, will be correlated with ORR, as well as with EFS at one year. Quantitative serum EBV levels will be monitored for the duration of treatment, and change in levels correlated with ORR, duration of response, and progression of disease.

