Patients achieving **PD** at first re-staging should be taken off treatment and treated with R-CHOP or similar chemotherapy at the discretion of the local treating investigator.

Patients achieving **SD** should likewise be taken off treatment and treated as above. However, at the discretion of the treating investigator, such patients may receive an additional treatment of the same termed "**Consolidation**".

Consolidation treatment is identical to Induction. If, after Consolidation treatment, these patients achieve CR or PR, they should proceed to Maintenance (see below for description). If, however, these patients are still SD or have progressed to PD, they should be taken off treatment and treated with R-CHOP or similar chemotherapy at the discretion of the local treating investigator.

Patients achieving **CR** or **PR** after the Induction course may receive an additional treatment of the same termed "**Consolidation**". Consolidation treatment is identical to Induction. For patients achieving CR after Induction, in whom avoidance of maintenance therapy is sought, Consolidation may be given as their final planned therapy. Patients who achieve CR after Induction may proceed directly to Maintenance therapy at the discretion of the treating investigator (for instance, if they are not likely to tolerate Consolidation therapy given the toxicity they experienced during Induction).

Following Consolidation, patients will proceed to **Maintenance:** 1.8 mg/kg IV infusion over 30 minutes once every 3 weeks (1 cycle = 3 weeks), for one year from starting induction or until progression of disease. At the discretion of the treating investigator, patients may discontinue brentuximab vedotin after 10 maintenance doses.

4.1.4 **Dose escalation on a per-patient basis (for both Phase I and Phase II):**

For any patient treated with a brentuximab vedotin dose of 0.8 mg/kg for 2 or more 21-day cycles without DLT, subsequent doses can be increased to 1.2 mg/kg, **but only at the discretion of the treating investigator.** *NOTE: the*

basis for escalation, or lack thereof, should be clearly documented in the Treatment eCRF.

4.1.5 Recommended treatment off study in the event of progressive disease or loss of response:

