6.2.1.2 Evaluable for Survival

All patients who have had at least one dose of study treatment will be evaluable for PFS and OS.

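### PFS has two event definitions (with and without death) and two time points, and graft rejection is counted over patients who may have no graft

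*Combined protocol and SAP*

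**What the plan says.** **PFS event.** Section 6.2.3 (the one headed Progression-Free Survival; Duration of Response carries the same number) reads "Progression-free survival (PFS) is defined as the duration of time from start of treatment to time of progression". It does not mention death and gives no censoring rule. Section 2.4.2 ends PFS at "tumor progression or death from any cause (whichever occurs first), with censoring of patients who are lost to follow-up". On the analysis set, 6.2.1.2 says "All patients who have had at least one dose of study treatment will be evaluable for PFS and OS". Section 10 contains no PFS analysis.

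**PFS and OS time point.** Objective 2.2.2 evaluates efficacy "as measured by PFS and OS at one year after the end of treatment". The Study Summary gives the same objective as "Further evaluate the efficacy as measured by one-year PFS and OS". Treatment lasts at most one year from first dose (4.0), can stop earlier for several reasons (4.6), and may end with Consolidation for some patients in CR (4.1.3).

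**Graft rejection.** Section 6.2.1.3 evaluates the rate in every patient who received a dose. The event in 2.4.6 requires a graft. Section 1.3 expects patients both with and without a solid organ transplant, and 3.1.1 and the note to 3.1.2 admit disease unrelated to transplantation.

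**The concern.** A patient who dies without progression is in the PFS analysis set by 6.2.1.2, has an event under 2.4.2 and has none under 6.2.3. Such deaths are possible here. Patients with stable disease at first re-staging "should likewise be taken off treatment and treated as above", that is, they move to R-CHOP or similar chemotherapy, and 1.1 quotes treatment-related mortality (TRM) of 13-50% with early chemotherapy. Reducing that mortality is central to the rationale in 1.3, so a PFS that ignores death omits events the trial cares about. OS would still record them, but the figure labelled PFS would be wrong.

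The two time-point statements can yield a one-year and a two-year figure for one objective. If 2.2.2 means each patient's own end of treatment, the time point differs between patients and no single Kaplan-Meier estimate corresponds to it.

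The graft-rejection denominator multiplies the rate among patients at risk by the share who have a graft. Graft rejection is listed as an efficacy objective, so the dilution favours the regimen.

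**Working it through.** The documents give no event counts, target rate or power for these endpoints, so there is no stated figure to reproduce. The figures below show scale on assumed counts, with N = 24 (Phase II enrolment, 10.2).

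**1. PFS definition.** Let p be progressions and d be deaths without progression before the time point, with complete follow-up. Under 2.4.2, S = (24 − p − d)/24. Section 6.2.3 gives no rule for deaths; assume they are censored. If the two kinds of event occur in constant proportion over time, the 6.2.3 value is exp(ln S × p/(p + d)). For p = 5:

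| d | 2.4.2 | 6.2.3 | Gap (points) | Gap over p = 3 to 10 |
|---|---|---|---|---|
| 0.6 | 76.7% | 78.9% | 2.2 | 1.9–2.3 |
| 1 | 75.0% | 78.7% | 3.7 | 3.1–3.9 |
| 2 | 70.8% | 78.2% | 7.3 | 6.1–7.8 |
| 3 | 66.7% | 77.6% | 10.9 | 9.0–11.6 |

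The row d = 0.6 is 24 × 1/40, from the sequential rituximab study cited in 1.3 "with rates of TRM (1/40 patients) that compare very favorably to historical rates".

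The order of events also matters. With p = 5, if all deaths come first, the 6.2.3 value is (24 − d − 5)/(24 − d); if they come last, it is 19/24 = 79.2%.

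- d = 1: 18/23 = 78.3% to 79.2%, gap 3.3–4.2 points
- d = 2: 17/22 = 77.3% to 79.2%, gap 6.4–8.3 points
- d = 3: 16/21 = 76.2% to 79.2%, gap 9.5–12.5 points

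**2. Time point.** Months from first dose = (day of last dose, counted from first dose, + 365.25)/30.44.

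- Stopped after the first dose: 365.25/30.44 = 12.0.
- Consolidation as final therapy: the fourth induction rituximab dose falls 21 days after the first dose, Consolidation starts 7–21 days later (5.1, footnote 7), and its fourth dose comes 21 days after that. The last dose is at 49–63 days, giving 13.6–14.1.
- Full year of treatment, or 2.2.2 read as the scheduled end: 730.5/30.44 = 24.0.
- If the end of treatment means the visit 21–28 days after the last dose (5.1, footnote 10), add 0.7–0.9.

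For scale, with a constant hazard, 12-month PFS of 60%, 70% or 80% becomes 0.60² = 36%, 0.70² = 49% or 0.80² = 64% at 24 months. For PFS, the actual-end reading matters only for patients who stop without progression, because a stop for progression is already an event.

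**3. Graft-rejection denominator.** Assume 3 rejections, with exact (Clopper-Pearson) 95% intervals:

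- 3/24 = 12.5% (2.7–32.4%), as 6.2.1.3 directs
- 3/18 = 16.7% (3.6–41.4%), if 18 have a graft
- 3/12 = 25.0% (5.5–57.2%), if 12 have a graft

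The graft share is not stated. If all 24 have grafts there is no dilution.

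**The case against.** The strongest reply is that the documents already point to one reading of PFS. Section 2.4.2 is the formal endpoint definition, 6.2.1.2 groups PFS with OS under survival, and 6.2.3 looks like an incomplete restatement. That may be the intent, but no text says so. Section 6.2.3 sits among the assessment rules an analyst would apply, and the neighbouring OS definition (6.2.4) does name death.

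It is also fair that the size is mostly assumed. The 1/40 rate comes from a different regimen and gives a gap of 2.2 points, less than one patient in 24 (4.2 points). The counts of 1 to 3 deaths have no source in the documents, and a death after the time point changes nothing. N could exceed 24, because 4.9 replaces some patients who have been dosed and 6.2.1.2 keeps them evaluable. These points limit the figures, not the conflict.

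On the time point, the synopsis gives no origin and could be shorthand for 2.2.2. Section 2.6 also uses one year (markers "will be correlated with ORR, as well as with EFS at one year"), but for a different endpoint, so it does not settle the matter. This part is an ambiguity rather than a proven contradiction, and it still needs one answer.

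On graft rejection, 2.4.6 lets patients at risk be identified, and nothing forbids an extra summary by graft status. The stated denominator is nevertheless all dosed patients.

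**Conclusion.** The point holds in all three parts. Section 6.2.3 as written yields time to progression, not the PFS of 2.4.2. On the assumed counts of 5 progressions and 1 to 3 deaths without progression in 24 patients, it reads about 3 to 12 points too high, and about 2 points at the cited 1/40 rate. There is no effect if no such death occurs before the time point. The time point may be anywhere from 12 to 24 months from first dose depending on how 2.2.2 is read. The graft-rejection rate is scaled down by the unstated graft share, for example by half if 12 of 24 have grafts.

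The textual faults are certain; the sizes are illustrations. These are secondary endpoints with no stated test, and the primary response analysis does not depend on them. They should be corrected before analysis so that the choices are not made with the data in view.

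**What to change.** 1. In the Progression-Free Survival section, replace the first sentence with the full 2.4.2 definition: from first dose to the earlier of progression and death of whatever cause, censoring patients lost to follow-up. Cite the section by title, since two share the number 6.2.3.
2. State one fixed Kaplan-Meier time point for PFS and OS, counted from first dose, in identical words in 2.2.2 and the Study Summary. Twelve months fits the synopsis and the 2.4.2 time origin; if the scheduled end of treatment was meant, write 24 months from first dose. Both lie within planned follow-up (4.7) and the three-year OS window (6.2.4).
3. In 6.2.1.3, report graft rejection among dosed patients with a graft in place at baseline, of any type covered by 2.4.6. Include those with allograft dysfunction or active rejection at entry, who count as events only on new or progressive rejection as 2.4.6 provides. Give the number with a graft and an exact 95% interval.

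**Cost.** A protocol amendment with IRB approval before implementation (11.7), and no added visits. Baseline graft status must be recorded; the schedule shows only history and physical examination, so confirm that the eCRF captures it. The graft-rejection interval will be wider wherever some patients have no graft, and reported PFS will be lower than under 6.2.3 if any patient dies without progression before the time point.
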